4.0 STUDY TREATMENT

4.1 NIDA Drug Supply Provision of Cannabis Product

We will be administering three cannabis doses to each participant using the vaporizer, including varying concentrations of CBD (low, medium, high): a) 2 vials of 0.01% CBD + 1.9% THC, b) 1 vial of 0.01% CBD + 1.9% THC and 1 vial of 5.1% CBD + 1.4% THC, and c) 2 vials of 5.1% CBD + 1.4% THC.

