To assess participant perception of drug effects, the Marijuana subscale (M-scale) of the Addiction Research Center Inventory (ARCI) will be administered⁶⁸. The M-scale has 12 true/false statements describing the subjective effects of marijuana (see attached ARCI Marijuana subscale). We have elected not to include a placebo in the current design because participants with prior cannabis use are likely to be aware they are not receiving the drug, given the lack of psychoactive/physiological effects, and this may confound their report of pain. We have also chosen to administer one fixed dose (8 puffs) to all participants to avoid the confound of varying levels of drug intake. Participants will be allowed to engage in normal activities, such as reading or listening to music between assessments. Participants will remain in the laboratory under direct observation by nursing staff for 3.5 hours after the vaporization inhalations are completed (30 minutes after the 180-minute sample collection). At that time a final vital sign status check will be made and upon satisfactory readings, the subject will be released and driven back to his/her domicile by taxicab or prearranged transportation.

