5.2 Toxicity

Our group has previously administered a similar dose of THC (3.5%) to participants in prior studies using both cigarettes (Wilsey B, Marcotte T, Tsodikov A, et al. A randomized, placebo-controlled, crossover trial of cannabis cigarettes in neuropathic pain. *J Pain*. Jun 2008;9(6):506-521) and vaporized cannabis (Wilsey B, Marcotte T, Deutsch R, Gouaux B, Sakai S, Donaghe H. Low-dose vaporized cannabis significantly improves neuropathic pain. *J Pain*. Feb 2013;14(2):136-148). In both studies his findings indicated that none of the participants receiving 3.5% THC exhibited any AE or SAE due to drug exposure. Based on the data he has collected, we do not anticipate AE or SAE due to acute THC exposure in the current study (1.4% to 1.9%). In addition, we will be recruiting participants with a history of cannabis use rather than cannabis-naïve individuals; therefore, there is also lower risk of a novel AE or SAE occurring in these participants.

CBD does not bind to the known cannabinoid receptors and its mechanism of action is yet unknown⁸⁶. The administration of CBD appears to be much less problematic compared to THC. In a recent study comparing oral THC, CBD, and placebo in healthy volunteers⁸⁷, CBD was well tolerated and there were no differences between oral CBD and placebo on symptomatic or physiological variables. Other work suggests that CBD may in fact attenuate some of the psychoactive effects of THC⁸⁸⁻⁹⁰. After an extensive literature review, Bergamaschi and

colleagues concluded that CBD is a substance with low toxicity⁹¹. Based on these findings, we do not anticipate that there will be AE or SAE due to acute CBD administration in the study. However, no specific research on vaporized combinations of THC/CBD has been performed and we will collect data at every visit on any adverse effects that occur.

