
time point. All response observations, including information from subjects who do not complete all experimental sessions, will be included in the analyses. Similar mixed-model analyses will be performed on the primary pain outcome after adjustment for psychomimetic side effects (measured with the ARCI scale) to assess for effects of the study drug on pain independent of subjective responses. The proportion of subjects with a 30% pain reduction, a standard for effective pain reduction⁶⁰ will be compared between each of the doses with chi-square tests; we will also calculate the number needed to treat (NNT) for a 30% pain reduction rate. We will also conduct analyses to examine the association between pain and EC biomarkers, including AEA, 2-AG, FAAH, and MAGL expression. A 5% significance level will be used for all testing. The association of pain levels with HRV will use a linear mixed-effects model, adjusting for potential confounders as above. Within-subject correlation will be accounted for using subject-specific random intercepts and slopes.

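### The ARCI-adjusted pain model conditions on a post-dose response that may differ by product, so its dose effect is free of subjective response only under assumptions the plan does not state

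*Combined protocol and SAP*

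**What the plan says.** Section 7.1 (Aim 1) models pain with dose, time and their interaction in a linear mixed model, followed by Tukey comparisons among doses. ARCI does not enter these models. The section then adds a further run: "Similar mixed-model analyses will be performed on the primary pain outcome after adjustment for psychomimetic side effects (measured with the ARCI scale". Its stated purpose is "to assess for effects of the study drug on pain independent of subjective responses".

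Section 4.2 describes the instrument: "To assess participant perception of drug effects, the Marijuana subscale (M-scale) of the Addiction Research Center Inventory (ARCI) will be administered". It adds that "The M-scale has 12 true/false statements describing the subjective effects of marijuana". No assessment times are given for it, and section 7.1 does not say whether it enters the model once per session or at each time point.

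Two other places bear on whether the score will differ by product:

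- Section 5.2: "Other work suggests that CBD may in fact attenuate some of the psychoactive effects of THC".
- Section 4.1 lists the low and medium conditions starting "a) 2 vials of 0.01% CBD + 1.9% THC, b) 1 vial of 0.01% CBD + 1.9% THC", with the medium condition completed by one vial at 5.1% CBD and 1.4% THC. The high condition is two vials of that second product.

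**The concern.** ARCI is not a baseline covariate. It records what the participant felt after the randomised product, so it lies downstream of dose. Holding it fixed compares sessions that are alike in subjective effect but received different products. If higher CBD lowers the score, a high-CBD session matched on ARCI to a low-CBD session will tend to be one in which something else pushed the score up, such as more THC absorbed that day or stronger expectancy. If that something also relieves pain, the adjusted comparison credits the relief to CBD. Randomisation had removed this imbalance and the adjustment brings it back.

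At stake is the reading of a supplementary result. As written, a significant adjusted dose effect would be taken as analgesia separate from feeling the drug. It could arise when the products relieve pain equally, and in the direction of the study's overarching hypothesis that more CBD reduces pain.

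**Working it through.** **Plan's own figure.** The documents give no number for the ARCI adjustment. The nearest is the power statement in section 7.4: n = 100, three doses, f = 0.180, 80% power. With zero correlation between sessions, λ = 0.180² × 100 × 3 = 9.72 on (2, 198) df gives power 0.797, so it reproduces. It serves here only to fix n = 100 and three sessions per person.

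**Why ARCI may differ by product.** Summed THC over two vials (section 4.1, assuming equal vial contents):

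- low CBD: 1.9 + 1.9 = 3.8
- medium CBD: 1.9 + 1.4 = 3.3
- high CBD: 1.4 + 1.4 = 2.8

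High against low: (3.8 − 2.8)/3.8 = 26% less THC. This and the CBD statement in section 5.2 point the same way. Neither gives a size for the change in ARCI.

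**Size of the bias.** Assumptions, none of them in the documents: *d* is the fall in ARCI from low to high CBD in session-level (within-person) SD, and *r* is the session-level correlation of ARCI with pain relief due to shared causes only. There is no true dose effect on pain, one value per session, dose is categorical and subject effects are removed.

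- Spurious high-versus-low benefit = *r* × *d*.
- Standard error = √[(1 − *r*²)(2/100 + *d*²/198)], where 198 = 99 × 2 within-person df.
- Two-sided rejection at 5% = Φ(z − 1.96) + Φ(−z − 1.96), with z = |*rd*|/SE.

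For *r* = 0.3 and *d* = 0.5: bias = 0.15; SE = √[0.91 × (0.02 + 0.00126)] = 0.139; z = 1.08; rejection about 19%. Simulations of the same model gave 17–20%.

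| *r* | *d* (SD) | spurious benefit (SD) | rejection, ARCI-adjusted |
|---|---|---|---|
| 0.1 | 0.2 | 0.02 | 5% |
| 0.1 | 0.5 | 0.05 | 6% |
| 0.2 | 0.3 | 0.06 | 7% |
| 0.3 | 0.5 | 0.15 | 19% |
| 0.5 | 0.8 | 0.40 | 86% |
| 0.3 | 0 | 0 | 5% |
| 0 | 0.5 | 0 | 5% |
| −0.3 | 0.5 | −0.15 (false harm) | 19% |

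In simulation the contrast without ARCI had mean about zero and rejected about 5% of the time in every row.

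**When the subjective effect itself relieves pain.** Let each SD of ARCI cause 0.3 SD of relief, with *d* = 0.5 and no direct dose effect.

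- No shared cause: the unadjusted contrast shows the high-CBD product worse by 0.3 × 0.5 = 0.15 SD. The adjusted contrast is about zero, which is the correct direct effect.
- Shared cause with *r* = 0.3 added: the unadjusted contrast still shows 0.15 SD worse. The adjusted contrast shows 0.15 SD better, so the sign reverses.
- No shared cause, but ARCI reliability 0.7: about (1 − 0.7) × 0.15 = 0.045 SD of the indirect difference stays in the adjusted contrast.

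**The case against.** The adjusted run is supplementary. The dose model, the time-point models and the Tukey contrasts all exclude ARCI, and nothing in the plan gives the adjusted result confirmatory weight. This stands, and it limits the point to one secondary interpretation.

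The bias also needs a shared cause. If relief simply follows from the subjective effect and nothing else links them, adjustment recovers the direct effect, as shown above. This stands too: a positive association between ARCI and relief is not by itself evidence of bias, and removing the indirect path is what a direct-effect question asks for.

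Section 4.2 uses cued puffs and one fixed dose to limit variation in intake. That should weaken absorption as a shared cause but cannot be assumed to remove it, and it does nothing about expectancy. The section gives two puff counts, 4 per session and a fixed dose of 8, which must be reconciled before the degree of standardisation can be judged.

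A reader might infer that the adjustment is the plan's safeguard for the blind and that participants can tell the products apart. The documents do not support this. Section 7.1 mentions neither blinding nor expectancy. The passage in section 4.2 stating that "participants with prior cannabis use are likely to be aware they are not receiving the drug, given the lack of psychoactive/physiological effects" explains why there is no placebo. It says nothing about telling apart three products that all contain THC.

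**Conclusion.** The interpretation attached to the ARCI-adjusted model is not justified as written. It depends on there being no unmeasured common cause of ARCI and pain and on error-free measurement of ARCI. The plan states neither and includes no sensitivity analysis. Where a shared cause raises both ARCI and relief, and ARCI falls with CBD, the model yields a false CBD benefit: 0.15 SD with about 17–20% false positives at the middle assumptions, close to nothing for weak correlations, and 0.40 SD with about 85% at the strongest setting. These rates are illustrative, because the documents supply neither input, and they are in session-level SD with one value per session.

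Two stronger readings are tempting. One is that the plan itself says CBD lowers the high; section 5.2 says only that it may attenuate some effects. The other is that an adjusted analysis can never address the question; a mediation analysis with declared assumptions could. The main dose comparison without ARCI is not affected by this problem.

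**What to change.** In section 7.1:

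1. State that the dose contrast without ARCI is the estimate of the dose effect on pain.
2. Analyse the M-scale as an outcome by dose with the same mixed model, and state when it is administered. This shows directly whether the products differ in subjective effect.
3. Replace the stated purpose of the adjusted run. Say that it is exploratory, conditions on a post-dose response, assumes no unmeasured common cause of ARCI and pain, and will not by itself support a CBD effect.
4. If the direct-effect question is to be kept, pre-specify a mediation analysis that adjusts for likely shared causes (for example session plasma THC, if measured) and includes a sensitivity analysis for unmeasured ones.

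Items 1 to 3 cost SAP wording and one extra model on data already to be collected. Item 4 needs more analysis work but no design change. The downside is a weaker secondary claim.

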2.0 STUDY DESIGN

Our objective is to assess 100 community-dwelling PLWH with neuropathic pain (PLWH-NP) who are recruited and tested at the HIV Neurobehavioral Research Program (HNRP)/Center for Medicinal Cannabis Research (CMCR) facilities located at the UCSD Medical Center. These participants will be enrolled in a study that consists of two stages: 1) administration of three different doses of vaporized cannabis obtained from NIDA (one dose per day on three separate days) that contain THC and varying concentrations of CBD, including: a) 2 vials of 0.01% CBD + 1.9% THC, b) 1 vial of 0.01% CBD + 1.9% THC and 1 vial of 5.1% CBD + 1.4% THC, and c) 2 vials of 5.1% CBD + 1.4% THC; 2) participation in a 6-month text message monitoring study, the Individual Monitoring of Pain and Cannabis Taken (IMPACT), where pain and cannabis use from local dispensaries is tracked. We will use a randomized crossover design where all participants receive each of the three cannabis doses at the HNRP and then are subsequently enrolled into IMPACT. We will recruit individuals who are currently using cannabis at least once a month to treat pain. The primary outcome measures of the study will examine: 1) the acute effects of NIDA-obtained cannabis on pain, EC levels, and the relationship with HRV (Aim 1); 2) the association between dispensary-obtained cannabis and changes in pain reported via IMPACT (Aim 2); 3) the effect of chronic THC and CBD exposure on longitudinal changes in pain, EC measures, and neurocognitive performance (Aim 3). Secondary and exploratory analyses will compare NIDA-obtained and dispensary-obtained cannabis effects on neuropathic pain and evaluate if there are different effects of reported cannabis strain (Sativa, Indica), specific cannabis products (e.g., OG Kush, Sour Lemon, etc.), or mode (smoking, vaporizing, ingesting food product) on pre-post drug exposure changes in pain

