7.0 STATISTICAL ANALYSIS PLAN

7.1 Aim 1 Measures and Analyses

Data will be assessed for normality and transformations applied as needed (e.g., log). Neuropathic pain before and after acute cannabis administration will be assessed by NPRS and the von Frey test. Plasma AEA and 2-AG will be measured with LC/MS. Flow cytometry will quantify the percentage of PBMC that express CB2, FAAH, and MAGL, including monocytes, CD4+ T-cells, and CD8+ T-cells. To examine the effect of different CBD/THC products on NP and EC biomarkers, we will use a linear mixed model with subjects treated as a random effect to model the response measures. This methodology takes into account the repeated measures aspect of the within-subjects crossover study design, incorporating information from observations for each subject at different treatment doses and multiple time points within each dose. For initial modeling, terms will include dose (0.01%, 5.1% - 4 puffs, and 5.1% - 8 puffs) CBD treated as a categorical variable), time (0, 60, 120 and 180 minutes after exposure treated as a continuous variable), and dose x time interaction. Additional terms will also be included for the sequence in which the treatments were administered (e.g., low CBD vs. medium CBD) and for second-order time (time²). The quadratic term is intended to model a U-shaped response curve if responses initially increase (or decrease), reach a maximum (or minimum), then decrease (or increase) back to baseline levels. For each outcome measure, each of these last 2 terms will be omitted from subsequent models and not reported if nonsignificant. Any potential factors that associate with outcome variables at the $\alpha = 0.20$ level in single-predictor analyses (history of light vs. heavy cannabis use, mode of prior cannabis use – i.e., engaging in smoking, or vaporizing, or both), time since last cannabis use before baseline, duration of cannabis use over lifetime, presence of adolescent cannabis use, duration of HIV infection, nadir CD4, viral load, gender, the presence of other non-cannabis analgesic medications, history of non-cannabis substance use disorders) will be included in the linear model. Dose effects at each time point will be assessed with mixed modeling after re-coding time as a categorical factor and including dose and dose x time terms (plus a term for sequence if this is significant in the initial model). Differences among doses will be evaluated using the Tukey honestly significant difference (HSD) comparison tests for differences of effects over all time points and contrasts within each

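### Responder rates at the three doses come from the same participants, but the plan compares them with chi-square tests that ignore the pairing and probably lose power

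*Combined protocol and SAP*

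**What the plan says.** Section 2.0 (Study Design) fixes the design for Aim 1: "We will use a randomized crossover design where all participants receive each of the three cannabis doses at the HNRP". Each participant can therefore have a responder status at the low, medium and high CBD dose.

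Section 7.1 (Aim 1 Measures and Analyses) analyses the continuous outcomes with a linear mixed model with participant as a random effect. The stated reason is that this approach "takes into account the repeated measures aspect of the within-subjects crossover study design".

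Later in the same section the responder outcome is introduced: "The proportion of subjects with a 30% pain reduction, a standard for effective pain reduction" is the quantity, and the rates "will be compared between each of the doses with chi-square tests". A number needed to treat (NNT) is to be calculated from the same outcome. No McNemar test, Cochran's Q, conditional or mixed logistic model, or GEE is named for it. Two other sentences in 7.1 bear on the point: "All response observations, including information from subjects who do not complete all experimental sessions, will be included in the analyses", and "A 5% significance level will be used for all testing".

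**The concern.** An unqualified chi-square test between doses is ordinarily the Pearson test on a two-by-two table of dose by response, which treats the two rows as different people. Here they are the same people. The variance that Pearson uses leaves out the covariance between a participant's two responses, so the standard error is wrong whenever that covariance is not zero.

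Positive covariance is the likely case. The same person with the same chronic condition inhales three products of similar THC content (1.4% to 1.9%), and someone who responds to one is more likely to respond to another. The Pearson standard error is then too large, the test rejects too rarely, and a real dose difference can be missed. The plan calls a 30% reduction a standard for effective pain relief and attaches an NNT to it, so this is the result that clinicians will read most easily. It should not lose the advantage that the crossover was chosen to provide.

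**Working it through.** **Plan's own figure.** Section 7.4 gives no power for the responder comparison. Its Aim 1 figure concerns the continuous AUC of pain change: 80% power at f = 0.180 with n = 100, and 0.185 and 0.190 at 95% and 90% completion. A one-way ANOVA with three independent groups of n, alpha 0.05 and noncentrality 3nf² returns f = 0.1801, 0.1848 and 0.1900, so those figures reproduce. They say nothing about responders, which need a separate check.

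**Inputs.**
- n = 100 participants, hence 100 pairs for any two doses (section 7.4).
- Alpha 5% (section 7.1), taken as two-sided; the plan does not state sidedness.
- Responder rates by CBD dose: not in the documents. Section 1.1 gives 34–40% on THC cannabis and 17–20% on placebo. The rates below are assumptions near those values.
- Phi: not in the documents. Assumed 0, 0.1, 0.2, 0.3 and 0.5.

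**Size of the test.** With equal rates p at two doses, the true variance of the difference in proportions is 2p(1−p)(1−phi)/n, while Pearson uses 2p(1−p)/n. The true two-sided size is therefore about 2·[1 − Φ(1.96/√(1−phi))]. At phi = 0.3, 1.96/√0.7 = 2.343, which gives 1.9%. At phi = 0.5, 1.96/√0.5 = 2.772, which gives 0.6%. Simulation of 400,000 trials per setting at 35%/35% agrees:

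| phi | 0 | 0.1 | 0.2 | 0.3 | 0.5 |
|---|---|---|---|---|---|
| Chi-square, true size | 5.0% | 3.9% | 2.9% | 1.9% | 0.6% |
| McNemar, true size | 5.0% | 4.9% | 5.0% | 5.1% | 5.4% |

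**Power, one setting by hand.** Take 35% versus 50% and phi = 0.3.
- Both respond: 0.35×0.50 + 0.3×√(0.35×0.65×0.50×0.50) = 0.175 + 0.072 = 0.247.
- Discordant cells: 0.35 − 0.247 = 0.103 and 0.50 − 0.247 = 0.253, together 0.357 before rounding.
- True standard error of the difference: √[(0.357 − 0.15²)/100] = 0.0578.
- Pearson needs a difference of 1.96×√(2×0.425×0.575/100) = 0.137. Power = Φ[(0.150 − 0.137)/0.0578] = 59%.
- McNemar needs 1.96×√(0.357/100) = 0.117. Power = Φ[(0.150 − 0.117)/0.0578] = 72%.

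Simulation gives 60% and 73%.

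**Power over the range** (35% versus 50%; McNemar without continuity correction; GEE with robust variance and terms for dose and period, from 20,000 three-dose trials with 42.5% assumed at the middle dose):

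| phi | 0 | 0.1 | 0.2 | 0.3 | 0.5 |
|---|---|---|---|---|---|
| Chi-square, 5% | 58.7% | 59.1% | 59.7% | 60.3% | 62.1% |
| McNemar, 5% | 57.0% | 61.5% | 66.7% | 72.9% | 87.5% |
| GEE, 5% | 57.1% | 62.2% | 67.2% | 73.1% | 86.8% |
| Chi-square, 5%/3 | 42% | 41% | 41% | 40% | 38% |
| McNemar, 5%/3 | 39% | 44% | 50% | 57% | 75% |

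**Other contrasts** (5%, chi-square then McNemar, at phi 0, 0.3 and 0.5):
- 34% versus 20%: 61/61%, 63/77%, 65/90%.
- 40% versus 30%: 32/31%, 28/42%, 25/57%.

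**Incomplete sessions.** Assume 10% of sessions are missing at random, which leaves about 0.9² = 81% complete pairs. For 35% versus 50% at phi 0, 0.1, 0.2, 0.3 and 0.5:
- Chi-square: 53%, 54%, 54%, 54%, 54%.
- McNemar, complete pairs only: 49%, 52%, 58%, 64%, 79%.
- GEE: 53%, 57%, 61%, 66%, 79%.

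GEE size was 4.8% to 5.5% with complete data and 4.9% to 5.2% with missing sessions.

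**The case against.** - **McNemar's statistic is also referred to a chi-square distribution**, and the section plainly knows that the design is within-subject. A paired test may have been meant. That is possible, but the text does not say so, and the ordinary reading is Pearson. McNemar would also drop incomplete pairs.
- **The gain depends on assumptions.** This stands. Phi is unknown, and dichotomising weakens correlation: under a bivariate normal model with 35% and 50% responders, phi 0.3 needs a correlation of about 0.47 between the underlying change scores, and phi 0.5 about 0.74. At phi 0.1 and 0.2 the gain is only about 2 and 7 points. It also varies with the contrast: at phi 0.3, 35% versus 45% gives 27% and 40%, and 35% versus 55% gives 87% and 93%. If phi were negative, chi-square would have slightly more power (58% against 53% at -0.1), but its true size would be about 6.2%.
- **The error is conservative and the analysis is supporting.** Both are true for positive correlation. They limit the severity but do not make the test right for the design.
- **The responder time point is undefined.** Section 7.1 lists 0, 60, 120 and 180 minutes and does not say when a 30% reduction is judged. This also stands. It affects the chi-square test equally, and it must be settled before any model is written.
- **The sentence about keeping all observations precedes the responder sentence** and may not be meant to govern it. Applying it to both is a reading, though a natural one.

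**Conclusion.** The concern holds. As written, the responder test does not fit the crossover, and it departs from the repeated-measures reasoning that the same section gives for its mixed model. With 100 participants and phi between 0 and 0.5, the nominal 5% test really operates at between 5.0% and 0.6%. Moving to a paired or clustered analysis changes power by about -2 to +25 points for 35% versus 50%, and by up to about +32 points for 40% versus 30%. At phi 0 there is no size error and nothing to gain.

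These sizes rest on assumed responder rates and an assumed phi. The direction needs only positive within-person correlation, which is plausible here. The mixed-model comparison of pain is unaffected. The change should be made, but it does not threaten the main Aim 1 result.

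**What to change.** Replace the chi-square tests with a GEE (robust variance) or a mixed logistic model for responder status, with participant as the cluster and terms for dose and period. Report the pairwise dose contrasts from that model. It uses every session that a participant completes. Keep pairwise McNemar or Cochran's Q only as a complete-case sensitivity analysis.

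In the same edit, state the post-dose time at which a 30% reduction is judged. If it is judged at every time point, add time terms. If an interval is given for the NNT, derive it from the within-participant risk difference. The plan states no such interval, and with complete data the NNT point estimate does not change. If McNemar was intended all along, the plan should name it and say how incomplete participants are handled.

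The cost is about a sentence of analysis-plan wording, plus the time-point definition, and a different software call. No additional data or participants are needed.
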